### **Background and Significance**

Historical background

#### *Role of microglia in MS:*

Multiple sclerosis (MS) is primarily a demyelinating disease of the central nervous system (CNS), but many patients also undergo progressive atrophy, especially in the gray matter (GM). GM atrophy plays a particularly prominent role in cognitive and physical decline in MS. White matter (WM) demyelination is also correlated with cognitive and physical impairment, albeit GM pathology accounts for the most variance in predicting cognitive and physical impairment.

Both neuroinflammation and neurodegeneration occur during all stages of MS. Axonal loss underlies especially the transition from relapsing to progressive MS, but neurodegeneration with axonal transections is known to be present already early in the disease. By studying progressive MS, one may thus gain important insights about the degenerative component of MS present in all stages of the disease.

Microglia are myeloid cells of the CNS are derived from early embryonic erythromyeloid progenitor cells and have migrated into the developing nervous tissue, where they have begun the maturation process into brain-resident microglial cells. Microglia constitute approximately 10% of the total cell population in a human brain. The key tasks performed by microglia include phagocytosis of extracellular debris, antigen presentation to host immune cells, and secretion of inflammatory mediators.

In the early phase of MS, microglial activation promotes the recruitment of naïve T cells, which are activated in the periphery by dendritic cells functioning as antigen-presenting cells. Microglia also act as antigen-presenting cells, re-stimulating the auto-reactive memory-T-cells invading through the blood-brain barrier (BBB) into the CNS. This is considered a key event in maintaining the chronic inflammation in the CNS. In active WM lesions, there is a profound infiltration of activated microglia and blood-borne macrophages throughout the lesion, whereas in slowly expanding (smoldering) or chronic active lesions, the microglia and macrophages are concentrated as a dense rim

around the lesions. Microglia have also been found diffusely in WM and GM with concomitant axonal degeneration and meningeal inflammation. Thus, chronic activation of microglia has been linked to neurodegeneration in the progressive phase of the disease. In progressive MS disease, activation of microglia has been detected in areas of the brain which appear normal in conventional MRI, the so called normal appearing (NA) WM (NAWM) and NAGM. When microglia are activated following an insult, they become mobile and capable of phagocytosis and antigen presentation. The phagocytosis of debris by microglia is thought to be essential for enabling the return of normal tissue homeostasis after an insult. In chronic neuroinflammation, the equilibrium between debris-clearing and inflammation-propagating microglia becomes unbalanced, and the hyper-activated microglia cause uncontrolled neuronal damage resulting in a self-propagating vicious cycle and progressive neurodegeneration. It is thus possible that prolonged inflammation related to activated microglia is one of the driving forces of the chronic progression of MS disease.

#### *Imaging of microglia activation using positron emission tomography:*

Positron emission tomography (PET) imaging enables molecular and neuroreceptor imaging in vivo. Particularly relevant for the study of MS is PET imaging of activated microglia. Here, several radioligands binding to the 18 kDa translocator protein (TSPO)—a protein structure expressed on the outer mitochondrial membrane of activated, but not resting microglia—have been developed. Activated microglia express TSPO, earlier called the peripheral benzodiazepine receptor (PBR) on the outer membrane of mitochondria. Several functions have been attributed to TSPO, either directly or indirectly, including immunomodulation, regulation of cholesterol transport, synthesis of steroid hormones, apoptosis, cell proliferation, porphyrin and anion transport, regulation of mitochondrial functions and heme synthesis. Two archetypal ligands binding to TSPO have been identified, namely Ro5-4864, the 4-chloro-derivative of diazepam, and PK11195, the isoquinoline carboxamide, the latter having been used as a marker for in vivo PET imaging of activated microglia. Numerous second-generation TSPO radioligands with higher affinity and specificity than their predecessor [11C](R)-PK11195 have been recently developed. F-PBR06 is a second-generation TSPO ligand with promising imaging characteristics. Recent studies showed increased F-PBR06 uptake corresponding specifically to activated microglia in animal models. A robust approach for quantitative in vivo assessment of specific F-PBR06 binding to TSPO has recently been developed. The Singhal et al. study demonstrated that quantitative TSPO PET with a second-generation F-PBR06 can be used to characterize innate immune responses in MS in vivo and provides further evidence supporting an association between the WM TSPO PET signal in lesions and disease severity. This approach is practical for extension to studies of the role of the innate immune response in MS for differentiation of anti-inflammatory effects of new medicines and their longer-term impact on clinical outcome.

#### Rationale and potential benefits

There has been an increasing recognition of the role of B-cells in the pathogenesis of MS since the initial description of intrathecal immunoglobulin synthesis in 1950. In MS, B-cells are present in parenchymal

lesions, tertiary follicle like structures in the meninges and cerebrospinal fluid where they are known to undergo clonal expansion. B-cell directed therapies using anti-CD20 antibodies have been shown to be highly efficacious in preventing relapses in RRMS and slowing progression in primary progressive MS although their mechanisms of action are not clear. In animal models, targeting B-cells using antiCD20 antibodies led to reduction in microglial activation and lesion formation. In fact, there was greater effect of anti-CD20 antibodies on microglial activation and lesion formation in the antibody independent model implying that the mechanism of action of these therapies extends beyond antibody production and may involve their actions on microglia. However, there is no human data to date exploring this hypothesis. Ofatumumab is a fully human anti-CD20 antibody that has recently been studied for treatment of relapsing MS in multiple phase II and phase III randomized controlled trials (ASCLEPIOS I and II).

Prior studies using Ofatumumab have demonstrated the time course of B-cell depletion in the periphery. There was 50% reduction by week 2, and >80% reduction by week 4 after administration of Ofatumumab at various doses. Ofatumumab demonstrated high efficacy for relapse rate reduction, new lesion formation and serum neurofilament light chain level reduction in multiple sclerosis patients as compared to an active comparator arm of teriflunomide (Aubagio). Additional secondary endpoints were also met, where ofatumumab showed a relative risk reduction in both 3-month confirmed disability (CDP) and in 6-month CDP versus teriflunomide in a pre-specified pooled analysis. Ofatumumab was found to be safe in MS patients.

However, the effects of Ofatumumab on microglia in the brain in MS patients are not known at this time. It is important to study the effect of anti-CD20 therapies on the innate immune system to understand their role in limiting disease progression in MS. We aim to assess the relationship between peripheral B-cell depletion and changes in microglial activation, after administration of Ofatumumab.

We aim to assess the effect of Ofatumumab on microglial activation using [F-18]PBR06 PET in MS patients in relation to changes in serum markers, MRI abnormalities and clinical impairment longitudinally over 9 months.

### **Specific Aims:**

Specific Aim 1: To determine the effect of Ofatumumab on microglial activation in MS over 9 months.

Specific Aim 2: To determine the time course of effect of Ofatumumab on microglial activation and its relationship with peripheral B-cell depletion, serum neurofilament light (sNFL) chain and glial-fibrillary acid protein (GFAP) levels and other serum biomarkers

Specific Aim 3: To determine the relationship of PET changes following Ofatumumab initiation with 3T MRI changes and clinical parameters.

## **Design:**

This is an open-label, observational, prospective, 9-month follow-up study to assess the efficacy of ofatumumab on microglia pathology in patients with MS, as measured by changes in microglial activation in the lesional and non-lesional, normal appearing white matter, cortical and subcortical grey matter, and peri-plaque area of chronic lesions in the brain.

### **Initial Visit:**

During the first visit, subjects will be administered the screening questionnaire (if that has not already been done over telephone). Subjects will review and eventually sign the consent form. They will be administered a physical examination, clinical assessment and standardized questionnaires for cognitive testing and/or other co-morbidities. In addition, blood samples will be drawn for genotype testing, infection screening, complete blood count and liver function test.

Demographics, physical examinations and neurologic assessments will be conducted at Brigham MS Center, Brigham and Women's Hospital, [name].

### **Genotype Testing:**

Blood sample drawn on the initial screening visit will be used to obtain genomic DNA for genotyping for polymorphism within the TSPO gene on chromosome 22q13.2, using a Taqman assay. High affinity and medium affinity binders will be included in the study, whereas low affinity binders will be excluded from the study.

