### Sample size and statistical considerations:

We will recruit 10 subjects, and each subject will undergo PET evaluations at day 0 (baseline), day 5, day 28, day 90 and day 273. The change with time in PET uptake in the lesional and normal appearing white matter, cortical and subcortical grey matter, and peri-plaque area of chronic lesions will be estimated using an analysis of response profiles model including a categorical effect of time and an unstructured covariance matrix for the residuals. This approach allows any change with time and places no structure on the covariance matrix. The primary analysis will be the global comparison across the five time points. If a significant difference among the five time points is observed, we will estimate the

change between day 0 and each of the other measurements, and we will correct for four multiple comparisons using a Bonferroni correction. Since the analysis of response profiles model estimates the parameters using maximum likelihood with the *mixed* command in Stata, this approach will handle missing data that is missing at random. Therefore, subjects who are missing one or more measurement will be included in our analysis. A p-value  $<0.05$  will be considered statistically significant.

In addition to the primary analysis of the change with time, we will also compare the change in PET uptake with the change in other measured variables (MRI, clinical, and immunologic measures). All of the remaining variables will be measured at the same time points as PET uptake (days 0, 5, 28, 90 and 273). First, we will calculate the change from day 0 to each of the other time points for each of the measures, and we will estimate the correlation between the changes using Pearson's correlation coefficient. This analysis will fit several models, but the interpretation of these correlations will be easy to interpret. Second, we will fit a linear mixed model with PET uptake as the outcome and two predictors for each of the other measured variables. In particular, we will include (1) the day 0 measure and (2) the change from day 0 so that we can estimate both the cross-sectional and longitudinal association between the other measured variables and PET. Our focus will be the longitudinal association estimated using the second term. If a subject receives corticosteroids during the study period, we'll account for that in a multivariate analysis by adding it as a covariate.

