#### Sample size calculation:

No prior data regarding effect of Ofatumumab on microglial changes is available at this time. The sample size of 10 is based on the typical number of patients in published PET-MRI studies with the same tracer. With a sample size of 10 subjects, we will be able to estimate the mean change between any pair of time points with a standard error of 0.32 times the standard deviation of the change. Assuming a PET effect size of 1.1 noticeable in intracortical and leukocortical lesions, identified on combination of PET and 3T MRI, a sample size of 10 provides 85% power and alpha-error of less than 5% to detect a treatment response. This means that we will have a reasonable precision for the design of future studies.

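### TSPO genotype is collected but left out of the association mixed model, which costs precision in the cross-sectional PET coefficient; the primary time comparison is affected little or not at all

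*Combined protocol and SAP*

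**What the plan says.** Under Genotype Testing, every subject is genotyped at screening for the TSPO polymorphism, and "High affinity and medium affinity binders will be included in the study". Low-affinity binders are excluded there and again in the Exclusion Criteria. No other use of genotype is stated.

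The section on sample size and statistical considerations describes two analyses that matter here.

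- **Primary analysis.** This is a response-profiles model with categorical time and an unstructured covariance. A global test across the five time points comes first. For the follow-up contrasts with day 0, "we will correct for four multiple comparisons using a Bonferroni correction".
- **Association analysis.** Pearson correlations of changes come first. Then "we will fit a linear mixed model with PET uptake as the outcome and two predictors for each of the other measured variables": the day 0 value of the other variable and its change from day 0. The purpose is to "estimate both the cross-sectional and longitudinal association between the other measured variables and PET". The plan adds that its interest lies in the second, longitudinal term.

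Corticosteroid use is the only further covariate named. No analysis mentions genotype, a log scale or percent change. The PET measure itself is not defined; the PET Scanning section refers to earlier methods for the tracer.

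**The concern.** Excluding low-affinity binders, and citing a paper on mixed-affinity binding of TSPO ligands, implies that the sponsor expects affinity to influence the signal. High- and medium-affinity binders may then differ systematically in PET level.

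In a model with the PET level as outcome, the coefficient of the day 0 predictor is estimated by comparing subjects. A genotype difference that is not modelled becomes part of the residual variation between only 10 subjects. At stake is the precision of an estimate that the plan commits to report, although a baseline variable already in hand could remove that source of error.

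The change analyses raise a separate question: whether pooling the two genotypes on the raw scale also weakens the primary comparison.

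**Working it through.** **Inputs from the documents.** "We will recruit 10 subjects, and each subject will undergo PET evaluations at day 0"; "Assuming a PET effect size of 1.1 noticeable in intracortical and leukocortical lesions"; "a sample size of 10 provides 85% power and alpha-error of less than 5% to detect a treatment response"; and a mean change estimated "with a standard error of 0.32 times the standard deviation of the change".

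**Inputs assumed, because the documents give none.** Medium/high signal ratio k = 0.6 to 0.8; medium-binder fraction p = 0.5 (0.3 to 0.5 for the change analysis); within-genotype coefficient of variation (CV) 15 to 25%; true within-genotype correlation 0.6.

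**Step 1: the plan's own figures.** The standard error is 1/√10 = 0.316, which agrees with 0.32. A two-sided paired t-test at 0.05 with n = 10 and effect 1.1 has power 87.1% (noncentral t, 9 degrees of freedom, noncentrality 1.1 × √10 = 3.48). Multiplying n by 0.955, the efficiency of the signed-rank test, gives 85.1%. The stated 85% is therefore reproducible, and it contains no genotype input.

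**Step 2: cross-sectional coefficient.** Set the high-affinity mean to 1 and the medium-affinity mean to k, with a 5/5 split. The genotype share of between-subject variance is

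0.25(1 − k)² / [0.25(1 − k)² + CV²(1 + k²)/2],

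and the correlation of 0.6 is diluted to 0.6 × √(1 − share).

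- k = 0.6, CV 15%: 0.0400/(0.0400 + 0.0153) = 72%; diluted correlation 0.32; simulated power 12% without genotype, 40% with it.
- k = 0.8, CV 25%: 0.0100/(0.0100 + 0.0513) = 16%; diluted correlation 0.55; simulated power 38% without, 43% with.

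Giving both genotypes the same SD changes this little: 12–39% without and 43–44% with. The combined range is 12–39% against 40–44%.

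A simulation of the repeated-measures model, with an additive genotype gap in units of the within-genotype SD, points the same way:

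| Gap (SD) | SE of cross-sectional term, no genotype | SE with genotype |
|---|---|---|
| 1 | 0.36 | 0.33 |
| 2 | 0.46 | 0.32 |
| 3 | 0.60 | 0.32 |

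**Step 3: longitudinal coefficient.** In the same simulation its standard error is 0.118 without genotype and 0.117–0.118 with it.

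**Step 4: change from day 0, additive genotype effect.** If genotype adds a constant a to every PET value of a subject, the change is (PET at day t + a) − (PET at day 0 + a), and a cancels. The paired t statistics are identical with and without the shift.

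**Step 5: change from day 0, proportional genotype effect.** If medium binders' changes are multiplied by k, with the change SD set to 1, the effective standardised effect is

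d = 1.1(pk + 1 − p) / √[(pk² + 1 − p)(1 + 1.1²) − 1.1²(pk + 1 − p)²].

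For k = 0.6 and p = 0.5: d = 0.88/√(0.68 × 2.21 − 0.7744) = 0.88/0.853 = 1.03.

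| k (p = 0.5) | d | Power, 0.05 | Power, 0.05/4 = 0.0125 |
|---|---|---|---|
| 1.0 | 1.10 | 87.1% | 64.6% |
| 0.8 | 1.085 | 86.2% | 63.2% |
| 0.6 | 1.03 | 82.6% | 57.9% |
| 0.5 | 0.99 | 79.2% | 53.3% |

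Over k = 0.6 to 0.8 with 30 to 50% medium binders, power at 0.05 is 83–86%.

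**Step 6: Pearson correlations of change.** Under proportional scaling, simulated mean correlations on the raw scale are 0.52–0.57 for k = 0.6 to 0.8. With no genotype effect they are 0.55–0.58. On the log scale they are about 0.58.

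**The case against.** The strongest reply is that the affected coefficient is a by-product. The plan says its focus is the longitudinal term, and the secondary endpoints under Study endpoints/variables are all associations of change in PET; none is cross-sectional. This stands, and it limits the importance of the point. It does not remove the point, because the plan still undertakes to estimate the cross-sectional association.

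A second reply is that every magnitude is assumed. The documents give no signal ratio, genotype mix or coefficient of variation, and a normalised PET measure could remove some or all of the genotype effect. This also stands. At the mild end of the range the gain is only from about 39% to 43%, and power stays below one half even with genotype in the model.

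A reader might go further and infer that genotype compromises the primary analysis, so that the response-profiles model needs a genotype main effect and PET should be analysed on a log scale. The documents do not support this:

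- A main effect cancels from the time contrasts when data are complete, and no missing-data scenario has been worked out that would justify adding it.
- The 79% power figure needs a ratio of 0.5. It also concerns one paired test at 0.05, not the global five-point test.
- A log scale helps if genotype multiplies the whole signal. If absolute changes are equal in the two genotypes, it can do harm. In simulation with a 5/5 split, log-scale against raw-scale power was 0.85 against 0.88 at a baseline ratio of 0.6, and 0.80 against 0.87 at 0.5; there was no loss at 0.8. The plan does not say which form applies.

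**Conclusion.** The point holds within limits. Genotype is collected and no analysis uses it. Leaving it out of the association mixed model exposes the cross-sectional PET coefficient to avoidable between-subject error. Under the assumptions listed, power for that coefficient is roughly 12–39% without genotype and 40–44% with it. The size depends wholly on inputs that the documents do not give.

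The longitudinal coefficient is essentially unaffected (standard error about 0.118 either way under an additive effect). The effect on the primary time comparison is nil if genotype is additive. If it is proportional, single-contrast power falls from 87% to 83–86% at ratios of 0.6 to 0.8. To say that genotype swamps the cross-sectional association would be fair only at the strong end of the assumed range, and the stated power calculation is not overturned.

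**What to change.** 1. Add TSPO genotype (high versus medium) as a fixed covariate in the association mixed model. The data are already collected. The cost is a sentence in the analysis plan and one between-subject degree of freedom, which is noticeable but affordable with 10 subjects.
2. Report the number of high- and medium-affinity binders enrolled.
3. Define the PET measure and the scale on which it is analysed.
4. Run a log or percent-change version of the change analyses, including the correlations of change, as a sensitivity analysis only.

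The primary response-profiles model needs neither a genotype main effect nor a log scale on this account.

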### **PET Scanning:**

For this study, all subjects will undergo five separate visits for [F-18]PBR06 PET scans, one visit before starting Ofatumumab treatment (day 0 baseline) and four more visits at approximately 5, 28, 90 and 273 days after initiating treatment. During the PET scan visits, all women subjects of child bearing age will undergo a stat quantitative serum hCG pregnancy test and only women with a negative test will undergo the radiopharmaceutical injection. The radiotracers will be produced using standardized procedures. At the time of imaging, the subjects will be positioned in the gantry of a high-resolution PET/CT camera. Head alignment will be made, relative to the canthomeatal line, using projected laser lines whose positions are known with respect to the slice positions of the scanner. A head support apparatus will be used to minimize head motion. Dynamic data over 120 minutes for PET quantification will be acquired, according to previously described methods for the tracer.

### **MRI Scanning:**

All subjects will undergo five 3T brain MRIs with and without contrast, one before starting Ofatumumab treatment (day 0 baseline) and four more at 5, 28, 90 and 273 days after initiating treatment. All women will be queried about their pregnancy status, use of contraception and last menstrual period. If a woman is of child bearing potential, she will undergo a urine pregnancy test. Subjects will undergo intravenous gadolinium contrast administration, during all visits. Hence, all women of child bearing potential will undergo urine pregnancy testing for this study.

### **Clinical Follow-up Visits:**

Subjects will come in for five clinical visits, one visit before starting Ofatumumab treatment (day 0 baseline) and four more visits at 5, 28, 90 and 273 days after initiating treatment. However, if the patient meets all inclusion criteria at the screening visit, the screening and baseline visits may occur on the same day. During these visits, subjects will undergo a physical examination, clinical assessment and cognitive assessment. A blood sample will be drawn to determine levels of sNfL, GFAP and other serum biomarkers. Visits will be conducted under the supervision of PI and other board-certified neurologists. Any adverse event reported by the patient or observed by the investigator will be recorded and reviewed at each clinical visit.

